## 1.3 Rationale

Cirrhosis affects nearly 633,000 Americans, and HCC is a leading cause of death in nonsymptomatic patients with cirrhosis (5, 31, 32). Less than 5% of patients with cirrhosis and HCC are candidates for liver resection due to the high degree of underlying liver dysfunction, which makes liver transplantation (LT) the definitive and curative treatment of choice. In 2015, 15,000 person-years were spent awaiting LT in the U.S. and only 6,600 patients received LT, underscoring the major competition among patients with cirrhosis for LT. Although patients with HCC receive priority listing for LT if they meet Milan/United Network for Organ Sharing (UNOS)  $T_2$  criteria, the wait time often exceeds 1 year. Exacerbating the problem for patients with HCC, very recent changes to the national liver allocation policy (October, 2015) delay the assignment of Model for End Stage Liver Disease (MELD) exception points for 6 months after listing, and reduce the maximum value of exception points to 34 for those with HCC. MELD is a clinical score that is a validated predictor of survival among patients with advanced liver disease used to prioritize patients for LT, and exception points increase a patients MELD score and therefore chances for LT. These changes were intended to create a better balance in transplant opportunities between those with and without HCC, and allow observation of tumor behavior to avoid transplanting aggressive tumors too guickly. However, for patients with HCC, these policy changes translate to longer wait times and growing concern that the tumor biology may shift from less to more aggressive over time. "Bridging" locoregional therapies (LRTs) are utilized while a patient is on the waitlist for LT, however drop-out from the waitlist remains a problem largely due to tumor progression or recurrence to beyond accepted radiological criteria. For example, the cumulative recurrence rate 2–3 years after radiofrequency ablation (RFA), the most common LRT in patients with cirrhosis eligible for transplant, has been reported at 72%-80%. Novel therapeutics offered in conjunction with LRT that could achieve lower rates or delay time to recurrence, could maintain transplant candidacy for sufficient time to achieve treatment with LT.

## Hypothesis:

- 1.) Participants randomized to pravastatin will experience an increase from baseline to 12 months in time to recurrence (TTR) compared to placebo group.
- 2.) Compared to placebo group, participants randomized to pravastatin will have:
  - a. increase in recurrence-free survival
  - b. increase in overall survival
  - c. decrease in waitlist drop-off
  - d. decrease in liver stiffness
  - e. decrease in liver fat fraction
  - f. greater modulation (increase or decrease, depending on the marker) of circulating biomarkers
  - g. decrease in liver tissue markers related to HCC

## 2.0 STUDY OBJECTIVES

The objective of this randomized double-blinded, placebo-controlled Phase II trial is to examine the effects of pravastatin use versus placebo after 12 months of treatment on hepatocellular cancer (HCC) recurrence in 130 patients with liver cirrhosis, HCC meeting Milan Criteria or OPTN tumor downstaging criteria for tumor burden, and initial locoregional therapy (LRT) with adequate response.

## 2.1 Primary Objectives

To evaluate the effect of a pravastatin intervention versus placebo on the change in time to recurrence (TTR) from baseline to 12 months following treatment initiation.

## 2.2 Secondary Objectives

To evaluate the effect of a pravastatin intervention versus placebo at 12 months from baseline on:

- 1) Recurrence-free survival
- 2) Overall survival

- 3) Waitlist drop-off
- 4) Change in liver stiffness
- 5) Change in liver fat fraction
- 6) Change in serum biomarkers of monocyte/macrophage and stellate cell activation
- 7) Levels of liver tissue markers related to HCC

## 2.3 Endpoints

The overall objective of this trial is to examine the effects of pravastatin use versus placebo at 12 months from baseline (Study Visit 1) on TTR in high-risk patients with liver cirrhosis. Participants will be on the study drug from Study Visit 1 until the last study visit (Study Visit 6 at 12 months). Primary and secondary endpoints are measured radiographically and in biological samples.

## • Primary Efficacy Endpoint

Following the American Association for the Study of Liver Diseases-Journal of the National Cancer Institute guidelines for trial design in HCC, we have set our primary endpoint as TTR, according to the recommendation for Phase II studies that assess adjuvant therapies secondary to liver directed therapy (33). TTR will be defined as the time from randomization to the first occurrence of a documented HCC recurrence or HCC death, within the 12-month intervention and assessment period. Participants who experience death attributed to their underlying liver cirrhosis, or other cause, will be censored at death date. For participants who do not recur or die and are lost to follow-up prior to the 12-month study visit, analysis of TTR will be censored at their last date of evaluable scan before drop-out.

In this study, we will rely heavily on the mRECIST outcome guidelines and the Liver Imaging Reporting and Data System (LI-RADS) diagnostic algorithm for defining hepatic recurrence (34, 35), and central expert independent radiographic review by MedQIA.

Pathological Definition: Participants who receive a transplant will become ineligible at the time of transplantation. Recurrent HCCs may also be identified at time of transplantation during the examination of the explant by a pathologist. These "incidental" HCCs represent a sizable proportion, amounting to 22% of HCCs among those receiving a liver transplant. Thus, if transplantation occurs and a pathologically confirmed HCC is detected, we will examine these pathologically defined tumors as a **secondary** definition of recurrence.

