#### Criteria fulfillment will be confirmed by the *Imaging Charter* and MedQIA.

- **4.1.4** Initiation of LRT (according to clinical judgement) within 24 months prior to Screening Visit, with adequate response as determined by *Imaging Charter* and MedQIA.
- **4.1.5** ECOG performance status  $\leq$  1 (or Karnofsky  $\geq$  70%; see Appendix A)
- **4.1.6** AST (SGOT) & ALT (SGPT) ≤ 5x institutional ULN
- **4.1.7** AFP < 400 ng/mL
- **4.1.8** Ability to understand and the willingness to sign a written informed consent document and medical release
- **4.1.9** Agree to use adequate contraception (hormonal or barrier method of birth control; abstinence) prior to study entry and for the duration of study participation; for women who are able to become pregnant.
- **4.1.10** Willing and able to comply with trial protocol and follow-up

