## 9.3.1 Analysis of Primary Endpoint: TTR

The log-rank test will be carried out to compare the distributions of TTR between placebo and pravastatin groups and the Kaplan-Meier estimators will be presented graphically. Cox proportional hazards model will be fitted to the data where the explanatory variable of interest is the indicator of treatment allocation adjusting for clinical and demographic baseline covariates, including sex. Patients who did not experience HCC recurrence, or receive a liver transplant and are still alive at the end of the study will be right censored. Patients who are transplanted or die before HCC recurrence will be treated as a competing risk. A competing risk model for TTR will be used to estimate the cumulative incidence of TTR using time to transplant or death as a competing risk. The proportional hazards assumption will be tested graphically and analytically, and model diagnostics such as martingale and Schoenfeld residuals will be conducted to assess model adequacy. Violation of the proportional hazards assumption will be addressed by use of time-dependent covariates or extended Cox models. The possibility of collinearity among the explanatory variables will be reduced after careful assessment of the correlation matrix and condition index. Automatic variable selection methods in a multivariable Cox proportional hazards model such as stepwise, backward, and forward will be used as a guideline to identify sets of important predictors and a more rigorous approach based on a 4-step procedure outlined in Collett (2003) will be employed (55). Power. Preliminary data indicate that the 12-month RFS is between 57% and 78% in patients with: 1) Child Pugh A or B cirrhosis, 2) small HCCs (typically meeting Milan criteria) 3) liver directed therapy (typically RFA or resection), and 4) no other interventions (27, 56-59). Therefore, we will assume that the 12-month RFS in the control group is 65%. Assuming a common cumulative incidence of the competing risk events at 12 months of 20% (10% due to liver transplant and 10% due to death), a 42-month accrual time and 15-month follow up time, and 10% drop out, data from 47 patients per group achieve 80% power to detect a hazard ratio of 0.45 using a two-sided log-rank test with a 0.1 level of significance. This is equivalent to detecting a decrease in the 12-month cumulative incidence of disease recurrence from 35% in the control group to 18% in the treatment group, which is clinically meaningful. The choice of a type I error rate of 0.1 is appropriate for a randomized phase II trial since this can serve as a randomized screening design for a nondefinitive comparison of statin vs placebo (reference: Mandrekar and Sargent (2010)). We further assumed that TTR and time to death or transplant are independent and exponentially distributed. Statistical power was based on the formulas in Machin et al. (2008) and Pintilie (2006) and were carried out using PASS version 13 (60, 61).

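### The secondary explant definition of recurrence does not separate viable tumour in a lesion treated before randomisation from new tumour, so it may count persistence as recurrence

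*Combined protocol and SAP*

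**What the plan says.** Section 2.3 (Primary Efficacy Endpoint) bases TTR on imaging: mRECIST, LI-RADS and central independent review, within 12 months of randomisation. A paragraph on a pathological definition follows. It opens with "Recurrent HCCs may also be identified at time of transplantation during the examination of the explant by a pathologist", calls such tumours incidental, and describes them as "amounting to 22% of HCCs among those receiving a liver transplant". The rule itself comes next: "if transplantation occurs and a pathologically confirmed HCC is detected, we will examine these pathologically defined tumors as a" secondary definition of recurrence. It sets no condition on where in the liver the tumour lies, makes no comparison with the lesions known at entry, and gives no event date or time window.

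Three other places bear on this.
- **Entry (4.1.4):** "Initiation of LRT (according to clinical judgement) within 24 months prior to Screening Visit, with adequate response as determined by" the Imaging Charter and the central reader. Criterion 4.1.3 requires a diagnosed HCC before that therapy.
- **Rationale (1.3):** "Less than 5% of patients with cirrhosis and HCC are candidates for liver resection".
- **Primary analysis (9.3.1):** "Patients who are transplanted or die before HCC recurrence will be treated as a competing risk". The design assumes a competing-event incidence at 12 months of "20% (10% due to liver transplant and 10% due to death").

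Section 5.9 provides for specimens at any transplant during the five-year study, inside or outside the 12-month intervention period.

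**The concern.** The paragraph is motivated by tumours that nobody knew about until the explant was examined. This population is different: everyone has a known HCC that was treated before randomisation and, in most cases, probably not removed. If some of that tumour is still viable when the liver is explanted, a pathologist will confirm HCC and the rule as worded is met, although nothing has recurred during the trial.

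Two things are at stake, both confined to this secondary definition. First, false events that occur equally in both arms pull the comparison toward no effect. Second, the events need an explant, so an arm with more transplants has more chances to record one. The trial's own hypotheses make an imbalance conceivable: 1.3 hopes that delaying recurrence will preserve transplant candidacy, and less waitlist drop-off on pravastatin is a listed hypothesis.

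**Working it through.** **Inputs from the documents.** 65 randomised per arm (9.2). From 9.3.1: 12-month recurrence of 35% on placebo and 18% on pravastatin, hazard ratio 0.45, and competing events of 20%, half of them transplants, common to both arms.

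**Assumed input.** The share f of explants with viable tumour in a previously treated lesion. The documents give no such rate. I use 22%, 50% and 80%. The protocol's 22% is a share of HCCs among transplant recipients and refers to incidental tumours, so it serves here only as a convenient low value.

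**Step 1: reproduce the plan's 18%.** With constant hazards, control incidences of 35% and 20% give a total of 55% at 12 months. The total monthly hazard is −ln(0.45)/12 = 0.0665, split 35:20 into 0.0423 (recurrence) and 0.0242 (competing). On pravastatin the recurrence hazard is 0.45 × 0.0423 = 0.0191 and the total is 0.0433. The 12-month recurrence incidence is (0.0191/0.0433) × (1 − e^(−12 × 0.0433)) = 17.8%, which matches the stated 18%.

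**Step 2: number of explants.** 0.10 × 130 = 13 within 12 months, or 6.5 per arm. In the analytic sample of 94 it is 9.4.

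**Step 3: imaging recurrences.** Placebo 0.35 × 65 = 22.75; pravastatin 0.178 × 65 = 11.57. The ratio is 0.51.

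**Step 4: add 6.5 × f false events to each arm.** Transplant is counted here as a competing event before recurrence, so these are different patients from those in step 3.

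| f | added per arm | pravastatin | placebo | ratio |
|---|---|---|---|---|
| 0% | 0 | 11.57 | 22.75 | 0.51 |
| 22% | 1.43 | 13.00 | 24.18 | 0.54 |
| 50% | 3.25 | 14.82 | 26.00 | 0.57 |
| 80% | 5.20 | 16.77 | 27.95 | 0.60 |

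Using the rounded 18% leaves 0.51, 0.54 and 0.60 unchanged.

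**Step 5: the same on a hazard-ratio scale.** With HR ≈ ln(1 − p₁)/ln(1 − p₀), 18% vs 35% gives 0.46. At f = 22% the incidences are 20.2% vs 37.2%, the HR is 0.49, and about 8% of events are false (2.86 of 37.3). At f = 50% they are 23% vs 40%, the HR is 0.51, and 16% are false (6.5 of 41.0).

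**Step 6: dependence on transplant rate.** Suppose, purely as an assumption, that 15% of the pravastatin arm were transplanted against 10% on placebo. At f = 50% the ratio would be (11.57 + 0.15 × 65 × 0.5)/26.00 = 16.4/26.0 = 0.63, compared with 0.57 at equal rates.

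**The case against.** The strongest reply is that the rule should be read with its lead-in. The paragraph is about recurrent, incidental tumours, and a known, treated lesion is not incidental. That is a fair reading of the intent, but the sentence that does the work does not carry the restriction over. A pathologist or analyst applying it literally would count any confirmed HCC.

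A reader might infer that every participant still carries the index lesion and that residual tumour will be scored as recurrence. The documents do not support that. A fully necrotic lesion is not a confirmed HCC. Section 9.3.1 describes the reference patients as having "liver directed therapy (typically RFA or resection"), so resection cannot be ruled out, although 1.3 makes it uncommon. The Imaging Charter may require complete response at entry, and the Laboratory Manual may address how explants are handled; neither is available. May be counted is as far as the text goes.

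A reader might also infer that the primary result is biased, or that pravastatin will be penalised for producing more transplants. Neither is shown. Primary TTR rests on imaging, with transplant before recurrence handled as a competing risk, and 9.3.1 assumes a common competing-event incidence in the two arms.

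The size can also be challenged. The calculation adds explant events to imaging events, whereas 2.3 says only that these tumours will be examined, 9.3 specifies no such analysis, and the definition is absent from the numbered secondary endpoints. It also treats all the added events as residual tumour. These objections stand, and they make the figures illustrative.

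**Conclusion.** The point holds as a gap in a secondary definition. As worded, the explant rule can classify tumour present before randomisation as an on-study recurrence, and it can do so only in transplanted participants. The reach is small: about 13 explants within 12 months, and possibly more counted if the missing time window lets later explants in. For assumed residual rates of 22% to 80%, equal across arms, the 12-month ratio would move from about 0.51 to between 0.54 and 0.60, toward the null. This rests on the plan's 10% transplant rate, on pooling explant and imaging events, and on a residual rate that the documents do not supply. Primary TTR and its power calculation are unaffected. It is an inexpensive improvement, not a threat to the trial's main conclusion.

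**What to change.** Amend the pathological definition in 2.3 so that:
- explant HCC counts as recurrence only when it lies outside the lesion(s) treated before randomisation;
- viable tumour in a treated lesion is reported separately, with a sensitivity analysis that adds those treated lesions that central review had read as completely responded. This belongs in a sensitivity analysis because such a lesion may hold either a true local recurrence or residue that imaging missed;
- the definition is limited to the 12-month window used for TTR, with the event date stated. Later explants can still serve the tissue-marker objective;
- explant findings are shown by arm with the number transplanted as denominator.

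The rule should be fixed before unblinding. The cost is a short amendment and one field on the pathology form to match explant tumours to the entry lesion map. Central review already produces lesion contours (3.1.3), so the matching should be practical. The price is slightly fewer events under this definition, including any true local recurrences within treated lesions, which the sensitivity analysis partly recovers.

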#### • Secondary Efficacy Endpoints

Secondary endpoints include recurrence-free survival (RFS), overall survival (OS), waitlist survival, liver stiffness, liver fat fraction, circulating biomarkers, and liver tissue biomarkers. Differences in secondary endpoints will be compared in the pravastatin and placebo groups.

1) RFS: We will assess the effect of pravastatin on RFS. RFS will be defined as the time from randomization to the first occurrence of a documented HCC recurrence, within the 12-month intervention and assessment period.

2) OS: We will examine the effect of pravastatin on OS (defined as the time from randomization to death from any cause).

3) Waitlist drop-off: We will evaluate the effect of pravastatin on reducing waitlist dropout due to any of the following causes: 1) HCC progression outside of Milan/T2 criteria, 2) cirrhosis progression (too sick to transplant), or 3) death.

Participants who are delisted for other reasons (such as positive alcohol test) will be censored at date of delisting.

4) Change in liver stiffness: We will evaluate the effect of pravastatin on withinperson change in liver stiffness, as measured by magnetic resonance elastography (MRE) or FibroScan, between Study Visit 1 (0 month) and Visit 6 (12 month). Within-patient consistency is required between Study Visits 1 and 6 with regards to liver stiffness testing modality (MRE or FibroScan).

5) Change in liver fat fraction: We will evaluate the effect of pravastatin on withinperson change in liver fat fraction, as measured by MRI-proton density fat fraction (PDFF), between Study Visit 1 (0 month) and Visit 6 (12 month).

6) Change in serum biomarkers of monocyte/macrophage and stellate cell activation: We will examine the effect of pravastatin on change in serum biomarkers including cytokines, chemokines, soluble receptors, and proteins (specifically, IL6, TNF $\alpha$ , sTNFRII, IL18BP, sCD163, IL10, IL17, IL-8, CCL17, TGF $\beta$ ).

7) Levels of liver tissue markers related to HCC: We will examine the effect of pravastatin on levels of liver tissue markers related to HCC including those in the Wnt/ $\beta$ -catenin pathway (specifically,  $\beta$ -catenin and glutamine synthetase).

## 3.0 STUDY DESIGN SUMMARY

This is a Phase II randomized, double-blinded, placebo-controlled clinical trial including 130 patients with cirrhosis diagnosed with HCC recruited from Cedars-Sinai Medical Center (CSMC), Ronald Reagan UCLA Medical Center (UCLA), Northwestern Memorial Hospital (NWU), UCSF Medical Center (UCSF), or Emory University Woodruff Health Sciences Center (EU). We will randomize study participants 1:1 to daily pravastatin 40 mg or placebo, created to be identical in color, consistency, and appearance to pravastatin, for an intervention period of 12 months. We expect to have a final sample of 47 study participants on pravastatin and 47 on placebo after accounting for the competing risk of transplantation or death due to cirrhosis (Figure 3). Evaluations will be taken at baseline and at study visits 1-6. Screening data will be reviewed to determine subject eligibility. Subjects who meet all inclusion criteria and none of the exclusion criteria will be enrolled in the study.

The following treatment regimens will be used:

- Experimental treatment: 40 mg pravastatin (N=65).
- Placebo: (N=65).

Total duration of active participation will be 12 months. Total duration of the study is expected to be 5 years.

[figure not shown]

Figure 3. Study profile for the primary endpoint of time to HCC recurrence

## 3.1 Study Measurements.

Following is a brief description of study measurements.

#### 3.1.1 Non-laboratory Measurements

**Imaging review.** Review of medical record by research coordinator to identify imaging required for eligibility purposes (see section 4.1.3 and 4.1.4) or all imaging studies conducted since eligibility or since the last study visit. Images will be sent to MedQIA (see 3.1.3) for central imaging review.

**Medical history.** Detailed medical history, including past medical/surgical interventions, disease history, and relevant laboratory results, obtained via patient interview and/or review of medical records by a study physician or research coordinator.

**Concomitant medications review.** Review of all current concomitant medications, including start and stop dates, dose, frequency, route, and indication (if available/applicable), obtained via review of the medical record or by patient self-report by a study physician or research coordinator.

**Medication compliance review.** Participants will be asked if they missed any doses of the study medication, and the dates of all missed doses will be recorded.

**Physical assessment**. Physician-directed physical assessment. Each assessment will include an interval symptom history; ECOG performance status assessment; vital signs, including blood pressure, heart rate, respiratory rate, and temperature; weight; and assessment of liver disease sequelae (varices, ascites and encephalopathy).

**Health assessment.** RN-directed assessment, consisting of ECOG performance status assessment and vital signs (including blood pressure, heart rate, temperature; and weight)

**Baseline symptom assessment.** Assessment of symptoms presenting prior to start of study intervention (Study Visit 1), obtained via review of the medical record or by patient self-report, by a study physician or research coordinator. NCI Common Terminology Criteria for Adverse Events version 5.0 (CTCAE v5.0) term, start and stop dates, grade, and treatment will be recorded on the Baseline Symptom Log. Grade should be determined by a study physician. Symptom assessment includes:

- Upper respiratory infection
- Headache
- Abdominal pain
- Constipation
- Nausea
- Vomiting
- Mild muscle aches
- Any other symptoms

**Symptom/adverse event assessment.** Assessment of symptoms presenting after the start of study intervention (Study visit 1), obtained via review of the medical record or by patient self-report, by a study physician or research coordinator. CTCAE v5.0 term, start and stop dates, grade, treatment, attribution, action taken, outcome, and expectedness will be recorded on the Adverse Event Log. Grade, attribution, and expectedness should be determined by a study physician. Symptom assessment includes:

- Upper respiratory infection
- Headache
- Abdominal pain

- Constipation
- o Nausea
- Vomiting
- Mild muscle aches
- Any other symptoms

**Baseline risk factor questionnaire.** A structured questionnaire will be administered by the research coordinator via patient interview of approximately 45 minutes' duration. The interview will elicit information on detailed race/ethnicity; acculturation, quality of life; medical and medications history; alcohol and tobacco use; and anthropometry including weight at different decades of life.

**Follow-up risk factor questionnaire.** A shorter questionnaire will be administered by the research coordinator via patient interview to assess changes in exposures and behaviors between visits. The interview will elicit information on quality of life, medical and medications history, and alcohol and tobacco use.

